Relationship between postoperative hypoxemia and renin-angiotensin system in patients with stanford type A acute aortic dissection

Study design

This prospective observational study was approved by the Clinical Research Ethics Committee of Beijing Anzhen Hospital, Capital Medical University, Beijing, China (Identifier: 2021107X), registered at ClinicalTrials.gov (Identifier: NCT05055570), and performed from August 2021 to January 2022 at Beijing Anzhen Hospital, Capital Medical University, Beijing, China.

Methods

The patient inclusion criteria included age 18-80 years old, diagnosis of Stanford type A aortic dissection, and scheduled for emergency surgery. The exclusion criteria included preoperative hypoxemia, perioperative acute cardiac insufficiency (left ventricular ejection fraction, LVEF < 40%) and rejection of consent. The overall study patients were divided into the hypoxemia group and non-hypoxemia group according to the presence or lack of hypoxemia after surgery. Postoperative hypoxemia is defined by the oxygenation index (OI), which is the ratio of arterial partial pressure of oxygen to fraction inspired oxygen ($\text{PaO}_2 / \text{FiO}_2$), of less than or equal to 200 for two consecutive times within the first 24 h after operation.

Indicators and methods

Basic characteristics, intraoperative details, biochemical parameters and outcome results were obtained, and blood was collected after surgery for the measurement of ANG II and sACE2 concentrations. All samples were tested twice by ELISA, and the average value was used for analysis.

Statistical analysis

Statistical analysis was performed using IBM SPSS software version 26.0. Univariate analysis was first performed to identify the potential risk factors for postoperative hypoxemia. Normally distributed continuous variables with homogeneous variance were compared using Student's t test and otherwise using the Mann-Whitney U test. Categorical variables were compared using the chi-square test

or Fisher's exact test. Correlation analysis was performed using the Spearman rank correlation test. Multivariate logistic regression analysis was performed for factors with $P < 0.1$ or that were considered clinically important. The odds ratio (OR) was calculated with a 95% confidence interval (CI). A P value of less than 0.05 was considered statistically significant.

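### Does the exclusion for perioperative LVEF below 40%, which gives no assessment period, put the marker result at risk?

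*Combined protocol and SAP*

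**What the plan says.** The eligibility text in Methods is one sentence on entry (age, diagnosis, scheduled emergency surgery) and one on exclusion: "The exclusion criteria included preoperative hypoxemia, perioperative acute cardiac insufficiency (left ventricular ejection fraction, LVEF < 40%) and rejection of consent". No window, time point or measurement method is given for LVEF.

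The comparison groups come from the outcome: "The overall study patients were divided into the hypoxemia group and non-hypoxemia group according to the presence or lack of hypoxemia after surgery". Postoperative hypoxemia means an oxygenation index "less than or equal to 200 for two consecutive times within the first 24 h after operation".

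Under Indicators and methods, "blood was collected after surgery for the measurement of ANG II and sACE2 concentrations", with no exact sampling time.

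The Statistical analysis section names the t test, with skewed or heteroscedastic variables compared "otherwise using the Mann-Whitney U test", then chi-square or Fisher tests, Spearman correlation and multivariate logistic regression with odds ratios and 95% confidence intervals. It mentions no patient flow, no tally of exclusions and no sensitivity analysis. The study is described as already performed, from August 2021 to January 2022.

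**The concern.** Two adjacent criteria carry different timing words. Preoperative hypoxemia can only be a baseline finding. Perioperative cardiac insufficiency may be found before, during or after the operation. Patients qualify when scheduled for surgery, so a low LVEF found afterwards would remove someone already eligible, possibly within the same 24 h that define the outcome and near the time of the blood sample.

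Exclusion after entry matters when the chance of removal depends jointly on the marker and on the outcome. The odds ratio in the retained patients can then differ from the one in all eligible patients. In a modest sample, a few removed patients could also decide whether a P value falls below 0.05. Without counts by timing and hypoxemia status, a reader could not tell whether any of this applied.

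**Working it through.** The document gives no sample size, event count, number excluded or target effect, so there is no figure of the plan's own to reproduce. The two calculations below rest on assumed inputs and ask only how large an effect could be.

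**1. Effect on the odds ratio.** Let S be the probability of being retained, indexed first by marker (1 high, 0 low) and then by hypoxemia (1 yes, 0 no):

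OR observed = OR true × (S11 × S00) / (S10 × S01)

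Assume a base exclusion risk b in patients with low marker and no hypoxemia, multiplied by a for a high marker and by h for hypoxemia. Then S00 = 1 − b, S10 = 1 − ab, S01 = 1 − hb and S11 = 1 − ahb.

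- Only one of the two matters (a = 1 or h = 1): the terms cancel and the factor is 1.00 at any b.
- b = 5%, a = h = 2: (0.80 × 0.95) / (0.90 × 0.90) = 0.76 / 0.81 = 0.94.
- b = 5%, one doubles and the other triples: (0.70 × 0.95) / (0.90 × 0.85) = 0.665 / 0.765 = 0.87.
- b = 2%, a = h = 2: (0.92 × 0.98) / (0.96 × 0.96) = 0.98.
- b = 10%, a = h = 2: (0.60 × 0.90) / (0.80 × 0.80) = 0.84.
- b = 10%, one doubles and the other triples: (0.40 × 0.90) / (0.80 × 0.70) = 0.64. This needs 60% of one cell to be removed.

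The range runs from nothing to material, and the document supplies none of b, a or h.

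**2. Effect on a P value.** Take the Mann-Whitney normal approximation without ties or continuity correction, with n1 hypoxemic and n0 non-hypoxemic patients and the marker higher in the hypoxemic group:

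z = (U − n1·n0/2) / √(n1·n0·(n1 + n0 + 1)/12)

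Assume 100 patients, n1 = 33, n0 = 67 and two-sided P = 0.02 (z = 2.326):

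U = 33 × 67/2 + 2.326 × √(33 × 67 × 101/12) = 1105.5 + 2.326 × 136.42 = 1422.85

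*Worst case.* Every hypoxemic patient added back has the lowest marker rank, or every non-hypoxemic one the highest. U then stays at 1422.85 while the group sizes grow.

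| Added back | z | P |
|---|---|---|
| 1 hypoxemic | (1422.85 − 1139.0)/139.15 = 2.04 | 0.041 |
| 2 hypoxemic | (1422.85 − 1172.5)/141.87 = 1.76 | 0.078 |
| 2 non-hypoxemic | (1422.85 − 1138.5)/139.80 = 2.03 | 0.042 |
| 3 non-hypoxemic | (1422.85 − 1155.0)/141.49 = 1.89 | 0.058 |

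*Milder case.* Hypoxemic patients added at middle rank raise U by k × n0/2. Two such patients give P = 0.025 and five give P = 0.034. If two hypoxemic patients are added at random ranks, P reaches 0.05 in about 9% of draws.

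*Does hypoxemia status settle the matter?* Smallest number added back that can bring P to 0.05 or more in the worst case, at N = 60, 100, 200 and 300:

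| Assumed setting | Hypoxemic | Non-hypoxemic |
|---|---|---|
| 33% hypoxemia, P = 0.02 | 1, 2, 2, 3 | 2, 3, 4, 5 |
| 50% hypoxemia, P = 0.02 | 2, 2, 3, 4 | 2, 2, 3, 4 |
| 33% hypoxemia, P = 0.04 | 1, 1, 1, 1 | 1, 1, 1, 2 |

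The contrast between hypoxemic and non-hypoxemic exclusions in the first row disappears in the second and nearly disappears in the third. It reflects the chosen inputs and is not a general property.

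**The case for a change.** The strongest case for acting is that the gap is certain and closing it is cheap. The text does allow removal after entry, the outcome and the markers both arise after surgery, and only counts could place the study between a factor of 1.00 and something material. Even a deliberate postoperative exclusion ought to have a stated period and a tally. If nobody was excluded after surgery began, one line would end the matter.

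The description of the text stands, and so does the value of the counts to a reader. What does not stand is the step to a flaw in the plan:

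- No exclusion after the start of surgery is documented.
- The contrast between the two criteria is thinner than it looks. "The exclusion criteria included preoperative hypoxemia" fixes a phase of care but gives no oxygenation threshold or measurement time either. Two different words in one sentence fit a deliberately wider cardiac exclusion at least as well as an oversight.
- The criterion may be there to remove hypoxemia of cardiac origin, though the document does not say so. In that case, refitting the model with those patients and no LVEF term could bring back the confounding that the restriction takes out, and its result would be hard to read.
- The P value bound is univariate. It limits neither the adjusted odds ratio nor its confidence interval.

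**Conclusion.** No change to the plan follows. The phrase "perioperative acute cardiac insufficiency (left ventricular ejection fraction, LVEF < 40"%) lacks an assessment period, and exclusion counts are not mentioned. In a summary this short, of a study already carried out, both are details that investigators normally give in the eligibility text and patient flow of the report. If LVEF was assessed only before surgery, the matter is one of wording.

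The size of any effect cannot be read from the document. On assumed exclusion risks, the factor on the odds ratio is 1.00 when only the marker or only hypoxemia drives exclusion. It is 0.98, 0.94 and 0.84 when each doubles a base risk of 2%, 5% and 10%, and further from 1 under stronger assumptions. The P value example crosses 0.05 with two or three patients only at extreme marker ranks. From P = 0.02, adding back hypoxemic patients equal to 5% of the sample at middle rank leaves P at 0.030 to 0.042 for 50% down to 20% hypoxemia. From P = 0.04 the same step does cross 0.05 (0.056 to 0.073), but a result that close to the limit is fragile to almost any change in the sample. These figures show what is possible under assumptions. They do not show that the planned analysis is wrong or that another population would serve the question better.

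### Does defining hypoxemia by two consecutive low OI values, with no blood-gas schedule, call for a change to the outcome definition?

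*Combined protocol and SAP*

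**What the plan says.** The Methods section sets the threshold on PaO2/FiO2 and requires a value "of less than or equal to 200 for two consecutive times within the first 24 h after operation". That rule does two jobs. Patients are "divided into the hypoxemia group and non-hypoxemia group according to the presence or lack of hypoxemia after surgery", so it forms the comparison groups. It is also the outcome of the risk-factor work in the Statistical analysis section: "Univariate analysis was first performed to identify the potential risk factors for postoperative hypoxemia", followed by multivariate logistic regression.

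A blood-gas schedule would most naturally appear under Indicators and methods, which says: "Basic characteristics, intraoperative details, biochemical parameters and outcome results were obtained, and blood was collected after surgery for the measurement of ANG II and sACE2". The postoperative blood draw mentioned there is for the two biomarkers, not for blood gases. Nothing else in the document states when gases were taken, how many there were, or how far apart the two qualifying values had to be.

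**The concern.** A rule that needs two low readings in a row gives more opportunities to qualify when more readings are taken. For a patient whose OI fluctuates around 200, the label then reflects sampling frequency as well as oxygenation. With no minimum interval, a repeat gas minutes after a low one also counts as confirmation.

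Because the rule defines the outcome, every odds ratio depends on it. If sicker patients had more gases or more rechecks, and if severity is related to ANG II or sACE2, an association could appear where none exists. Adjustment would remove this only if the variable driving sampling was recorded and entered the model. The Statistical analysis section selects covariates by P < 0.1 or clinical importance and names none.

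**Working it through.** The document gives no OI distribution, gas frequency, event count or hypoxemia rate, so there is no figure of its own to reproduce. Its only inputs here are the threshold of 200, the two-consecutive rule and the 24-hour period. Everything else below is assumed.

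**1. Mechanism, independent gases.** Let p be the chance that one gas is at or below 200. Let a be the probability of no run so far with the last gas not low, and b the same with the last gas low. Start at a = 1, b = 0. Each gas updates a to (a + b)(1 − p) and b to (old a) × p. The chance of meeting the rule is 1 − a − b.

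For p = 0.5, (a, b) runs (0.5, 0.5), (0.5, 0.25), (0.375, 0.25), (0.3125, 0.1875), so 4 gases give 1 − 0.5 = 50%. Twelve gases give 91%. For p = 0.1 the figures are 3% and 10%.

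**2. Correlated OI.** Take a Gaussian OI with correlation exp(−time/τ), τ from 1 to 24 h, equally spaced gases and within-patient SD 50:

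| Mean OI | 4 gases | 12 gases |
|---|---|---|
| 150 | 88-93% | 96-100% |
| 230 | 18-29% | 47-62% |
| 250 | 7-16% | 27-38% |
| 300 | 0.2-1.9% | 1.1-5.6% |

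The dependence is real near 200 and fades away from it. A recheck 30 minutes after each low value, added to 4 scheduled gases, raises the 7-16% at mean 250 to 20-28%, or to 26-35% if a recheck of the last scheduled gas also counts.

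**3. Sensitivity to the within-patient SD.** At mean 250, one gas is low with probability Φ((200 − 250)/50) = Φ(−1) = 15.9% when the SD is 50, but Φ(−50/30) = Φ(−1.67) = 4.8% when it is 30. The 4 versus 12 comparison then falls to 0.7-4% versus 4-12%. In a mixed population (mean 250, between-patient SD 80), the odds ratio for being classified hypoxemic with 8 rather than 4 gases is:

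| Within-patient SD | Odds ratio |
|---|---|
| 50 | 1.3-1.6 |
| 30 | 1.2-1.3 |
| 20 | 1.1-1.2 |

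A narrower between-patient SD of 50, with within-patient SD 50, takes the upper end to 2.0.

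**4. Effect on a biomarker with no true association.** The odds ratios in step 3 are for gas count, not for ANG II or sACE2. To reach the biomarkers, both missing links must be assumed. With within-patient SD 50 and a true odds ratio of 1.00 per SD, the result is 1.02-1.16 if severity drives the number of gases and 1.01-1.22 if it drives rechecks. Adjusting for gas count works in the first case (0.995-1.008) but fails badly in the second (0.379-0.793), because there the count is partly a consequence of low values.

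**5. Would a fixed-window rule be better?** Take the first gas in each 6-hour window and require two adjacent windows at or below 200. With nearly every window filled, the null odds ratio is 0.998-1.015. Now let sparsely sampled patients have empty windows, treated as unable to qualify, with gas counts driven by severity and no rechecks. Two simulations with different assumed inputs give:

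| Mean gases | Plan's rule, run A | Window rule, run A | Plan's rule, run B | Window rule, run B |
|---|---|---|---|---|
| 7 | 1.07-1.18 | 1.04-1.06 | 1.04-1.15 | 1.02-1.06 |
| 5 | 1.11-1.25 | 1.19-1.21 | 1.04-1.19 | 1.12-1.17 |
| 4 | 1.11-1.24 | 1.26-1.30 | 1.05-1.18 | 1.18-1.22 |

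Run A used within-patient SD 50, biomarker-severity correlation 0.6 and at least 2 gases per patient; 7%, 28% and 42% of patients had an empty window. In run B, keeping only patients with all windows filled brought the odds ratio to 0.97-1.02 but dropped 3-42% of patients.

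**The case for a change.** The strongest case for acting is that the gap sits on the variable that defines both the groups and the outcome, and that another team could not reproduce the classification from the text. The document gives nothing to rule out severity-driven sampling, and a spurious odds ratio near 1.2 is not trivial in a study of association. Time-stamped gases, if retained, would allow a window rule beside the existing one with no new data collection.

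The omission and the mechanism both stand. So does the point that a window rule works well when sampling is dense enough to fill the windows. The step to a required change does not stand. That sampling differed, and that severity relates to the biomarkers, are plausible but unshown. The actual gas frequency is unknown, so one cannot say whether the window rule would help or harm. It also has a cost: in the assumed scenarios 21-31% of patients are called hypoxemic rather than 29-45%, with less power, and short episodes within a window are lost. Nor does it fix a minimum interval, since gases either side of a window boundary can still qualify.

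**Conclusion.** This is missing measurement detail, not a flaw in the outcome. If gases were taken on a common schedule, the rule gives a valid classification that is noisy near 200, and the second value already guards against a single stray reading. Bias needs two further conditions that the document does not show. Granting both, with a within-patient SD of 50, it is small to moderate: about 1.01-1.22 per SD against a true 1.00. The sampling effect that feeds it is weaker at smaller within-patient SDs. Its direction and size in this study cannot be computed from the document.

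Redefining the outcome has no assured gain. Keeping patients with empty windows can reproduce or enlarge the bias. Excluding them removes it in the simulation but may cost up to 42% of patients, a trade-off on which statisticians would differ. The gas times, the interval between qualifying values and the number of gases per patient in each group can be stated from the study records when results are reported. Only if those counts differed would a sensitivity analysis be worth discussing. No change to the plan follows.

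### Normal variables with unequal variances are sent to Mann-Whitney, which does not in general hold its level for equal means; Welch's t test does (minor)

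*Combined protocol and SAP*

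**What the plan says.** The Methods section forms the comparison groups by outcome: "The overall study patients were divided into the hypoxemia group and non-hypoxemia group according to the presence or lack of hypoxemia after surgery". Their sizes are therefore not set by design, and the document gives no split.

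The Statistical analysis section states the purpose of the univariate tests: "Univariate analysis was first performed to identify the potential risk factors for postoperative hypoxemia". For continuous variables the rule is "Normally distributed continuous variables with homogeneous variance were compared using Student's t test and otherwise using the Mann-Whitney U test". The results are used twice: they are read at the 5% level ("A P value of less than 0.05 was considered statistically significant"), and they control entry to the adjusted model ("Multivariate logistic regression analysis was performed for factors with $P < 0.1$ or that were considered clinically important").

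The document does not name the check of variance, the null hypothesis of the univariate tests, their sidedness, or Welch's test.

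**The concern.** Student's t test is reserved for variables that meet two conditions, normality and equal variances. A variable that is normal but fails the second condition falls to Mann-Whitney. The rule thus treats unequal spread as a problem, but its substitute test does not solve it.

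The variance in the Mann-Whitney statistic is derived for two identical distributions. If the means are equal but the spreads differ, the true variance of U differs from that value, and the rejection rate moves away from nominal. For normal data, equal means also imply equal medians and P(X<Y) = 0.5, so the same failure applies to those location hypotheses.

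At stake are the univariate P values of the affected variables and their entry to the logistic model through the P < 0.1 screen. The error can run either way: entry too easy or too hard.

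**Working it through.** **Inputs.** From the document: levels 0.05 and 0.10, and the test-selection rule. Everything else is assumed, because the document gives no figures: two-sided tests, normal data, equal means, total 100 unless stated, splits from 50:50 to 20:80, SD ratios from 1.25 to 3, and the asymptotic Mann-Whitney test without continuity correction. The plan has no figure of its own to reproduce.

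**Closed form (large samples).** Let group 1 be the smaller, with n₁ patients and SD s₁. Define vᵢ = asin[sᵢ²/(s₁²+s₂²)]/(2π). The ratio of the true to the assumed variance of U is

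r = (v₁/n₁ + v₂/n₂) / [(1/n₁ + 1/n₂)/12],

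and the actual level is 2[1 − Φ(z/√r)], with z = 1.960 at 5% and 1.645 at 10%.

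For an SD ratio of 2, the more variable group has v = asin(0.8)/(2π) = 0.1476 and the other has v = asin(0.2)/(2π) = 0.0320.

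- 30:70, smaller group more variable: r = (0.1476/30 + 0.0320/70)/0.003968 = 1.355. At 5%, 1.960/√1.355 = 1.684, giving 9.2%. At 10%, 1.645/√1.355 = 1.413, giving 15.8%.
- 30:70, smaller group less variable: r = (0.0320/30 + 0.1476/70)/0.003968 = 0.800. At 5%, 1.960/√0.800 = 2.191, giving 2.8%. At 10% the level is 6.6%.
- 50:50: r = (0.1476 + 0.0320)/50/0.003333 = 1.078, giving 5.9% and 11.3%.

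Only the split and the SD ratio matter in r, so a larger sample does not help.

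**Simulation.** 100,000 runs per setting; the standard error at 5% is √(0.05 × 0.95/100,000) = 0.07 percentage points. Rejection rates are in %.

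| Split | SDs, smaller:larger group | Mann-Whitney 5% / 10% | Student 5% | Welch 5% / 10% |
|---|---|---|---|---|
| 50:50 | 1.25:1 | 4.9 / 10.1 | 4.9 | 4.9 / 10.0 |
| 50:50 | 2:1 | 5.9 / 11.2 | 5.2 | 5.1 / 10.1 |
| 50:50 | 3:1 | 6.9 / 13.0 | 5.3 | 5.1 / 10.2 |
| 48:52 | 3:1 | 7.2 / 13.3 | 5.9 | 4.9 / 9.8 |
| 48:52 | 1:3 | 6.3 / 12.0 | 4.4 | 5.0 / 10.0 |
| 45:55 | 3:1 | 8.1 / 14.4 | 7.3 | 5.1 / 10.1 |
| 45:55 | 1:3 | 5.7 / 11.1 | 3.6 | 5.1 / 10.1 |
| 40:60 | 2:1 | 7.5 / 13.7 | 8.4 | 5.0 / 9.9 |
| 40:60 | 1:2 | 4.3 / 9.1 | 2.8 | 5.0 / 10.1 |
| 30:70 | 1.25:1 | 6.1 / 11.9 | 7.3 | 5.0 / 10.0 |
| 30:70 | 1:1.25 | 4.1 / 8.7 | 3.3 | 5.1 / 10.1 |
| 30:70 | 2:1 | 9.2 / 15.7 | 12.7 | 5.0 / 10.0 |
| 30:70 | 1:2 | 2.8 / 6.6 | 1.3 | 5.0 / 10.0 |

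With clear imbalance (40:60 or beyond), Mann-Whitney is too liberal when the smaller group is more variable and too strict when it is less variable, but it is closer to 5% than Student's t. Near balance, at SD ratio 3, it is too liberal whichever group is more variable, and it can be further from 5% than Student's t. At 30:70 with SDs 2:1, the 5% test runs at 9.1% with 60 patients and 9.2% with 200.

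**Whole rule.** The variance check is unnamed, so Levene's test at 0.05 is assumed. The table gives error at nominal 5%, in %. The minimal change puts Welch in the unequal-variance branch only. In the 20:80 rows, the two checked rules come from 20,000 runs.

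| Split | SDs, smaller:larger group | Current rule | Minimal change | Welch for all normal variables |
|---|---|---|---|---|
| 30:70 | 1.25:1 | 6.6 | 6.2 | 4.9 |
| 30:70 | 1.5:1 | 7.6 | 6.0 | 4.9 |
| 30:70 | 2:1 | 9.2 | 5.2 | 5.0 |
| 30:70 | 1:2 | 2.8 | 5.0 | 5.0 |
| 20:80 | 1.5:1 | 9.1 | 7.2 | 5.0 |
| 20:80 | 2:1 | 11.2 | 5.7 | 5.2 |

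**The case against.** The strongest objection is that the plan never says the univariate tests compare means. For a risk-factor screen, a natural null is that the variable is unrelated to hypoxemia, meaning identical distributions in the two groups. Mann-Whitney holds its level for that null, and a variable whose spread differs between groups is in a sense associated with the outcome. This stands as a limit: the error rates above concern differences in location only. It does not rescue the rule if a risk factor is read as a difference in level, which is the usual reading.

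Second, no affected variable can be identified. The 9.2% needs normality, a 30:70 split and a twofold SD ratio in the unfavourable direction, all together. This also stands; milder inputs give small errors.

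Third, at mild SD ratios much of the whole-rule error comes from variables that pass the variance check and go to Student's t, not from the Mann-Whitney branch. This is correct: at 30:70 with SDs 1.25:1, the minimal change moves 6.6% only to 6.2%. It bears on which remedy to choose, not on whether the branch is well chosen.

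Finally, the reach is narrow. The categorical tests, the Spearman analysis ("Correlation analysis was performed using the Spearman rank correlation test") and the logistic odds ratios and intervals do not use this test. Clinically important factors bypass the screen, and a variable that enters wrongly is still tested in the model. All of this is accepted and sets the rating.

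**Conclusion.** The concern holds and is minor. The rule sends normal variables with unequal variances to a test that does not in general hold 5% or 10% for equal means, although a test made for that case exists. The simulated departures range from negligible (4.9% at nominal 5%, balanced groups, SD ratio 1.25) to clear (9.2% or 2.8% at 30:70, SD ratio 2). The closed form and the simulation agree, and sample size does not remove the error.

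Confidence is high in the general statement. The effect in this study cannot be computed, because group sizes, SDs and the list of normal variables are not given; possibly no variable is affected.

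**What to change.** **Minimal change.** Replace the rule with: *Approximately normal continuous variables are compared by Student's t test if the group variances are judged equal and by Welch's t test if not; Mann-Whitney U is kept for variables that are not approximately normal.* Name the variance check. At 30:70 this removes nearly all the error at SD ratio 2, but some remains at milder ratios and stronger imbalance, as the whole-rule table shows.

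**Preferable option.** Use Welch's t test for every approximately normal variable and drop the variance check. This holds the level at the milder ratios too.

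**Cost.** One sentence, a re-run of the affected comparisons and of the P < 0.1 screen, and a refit of the logistic model only if a variable's entry changes. The minimal change leaves the equal-variance comparisons untouched. The option costs a little power when variances are equal and groups are very unequal. For an assumed 0.6 SD difference and 100 patients, Welch against Student gives 84.2% v 84.2% at 50:50, 82.6% v 82.7% at 40:60, 77.2% v 77.9% at 30:70 and 64.0% v 66.1% at 20:80. The loss is therefore 0.7 points at 30:70 and 2.1 points at 20:80.
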